8.3. Adverse Events and Serious Adverse Events

The definitions of an adverse event or SAE can be found in Appendix 3.

Adverse events will be reported by the participant.

The investigator and any qualified designees are responsible for detecting, documenting, and recording events that meet the definition of an adverse event or SAE and remain responsible for following up adverse events that are serious, considered related to the study intervention or study procedures, or that caused the participant to discontinue the study intervention (see Section 7).

The following expected adverse drug reactions are based on BOTOX clinical trial data for the treatment of GL and LCL (Tables 8-1 and 8-2, respectively).

Table 8-1 Expected Adverse Reactions for Treatment of Glabellar Lines

Expected Adverse Reactions ^a	Incidence
Eyelid ptosis	3%
Facial pain	1%
Facial paresis	1%
Muscular weakness	1%

^a Data are based on BOTOX glabellar lines clinical trial data (BOTOX Cosmetic US Package Insert, 2017)

Table 8-2 Expected Adverse Reactions for Treatment of Lateral Canthal Lines

Expected Adverse Reactions ^a	Incidence
Eyelid oedema	1%

^a Data are based on BOTOX lateral canthal lines clinical trial data (BOTOX Cosmetic US Package Insert, 2017)

The adverse drug reactions of eyelid edema, eyelid ptosis, facial pain, facial paresis, and muscular weakness with BOTOX are usually mild in severity, reversible, and have a low

Protocol MT10109L-004 AMD 5

incidence. Therefore, no treatment for these reactions is recommended. If these reactions are moderate or severe, medical help should be sought as needed.

8.3.1. Time Period and Frequency for Collecting Adverse Event and Serious Adverse Event Information

All adverse events will be collected from the signing of the ICF at the timepoints specified in the SoA (Section 1.3), and as observed or reported spontaneously by study participants until 30 days after the participant's last study visit.

Medical occurrences that begin before the start of study intervention, but after obtaining informed consent will be recorded in the adverse event section of the eCRF.

All SAEs will be collected from the signing of the ICF study at the timepoints specified in the SoA (Section 1.3), and as observed or reported spontaneously by study participants, until at least 12 weeks after the participant's last administration of MT10109L intervention.

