9.4.2.1. Adverse Events

_	

An adverse event that occurs more than 30 days after study exit will not be counted as a TEAE.

An adverse event will be considered a TESAE if it is a TEAE that additionally meets any SAE criteria.

The number and percentage of participants reporting TEAEs in each study intervention group will be tabulated by system organ class and preferred term and by system organ class, preferred term, and severity

The number and percentage of participants reporting treatment-related TEAEs in each study intervention group will be tabulated by system organ class and preferred term by MT10109L cycle.

If more than 1 adverse event is coded to the same preferred term for the same participant, the participant will be counted only once for that preferred term using the most severe and most related occurrence for the summarizations by severity and by relationship to MT10109L intervention.

Protocol MT10109L-004 AMD 5

Summary tables will be provided for participants with SAEs and participants with adverse events leading to discontinuation if 5 or more participants reported such events. Listings of all adverse events, SAEs, and adverse events leading to discontinuation by participant will be presented.

The definitions of an adverse event and SAE can be found in Appendix 3.

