## 5.1.1. Treatment Group and Treatment Cycles

All safety and efficacy analyses will be integrated analyses that include data from both the leadin studies and the MT10109L-004 extension study, for participants enrolled into the extension study.

A study treatment cycle is considered to start on the day of treatment with study intervention and end on the day prior to the next study intervention or on the study exit day if there are no subsequent interventions. The nomenclature used will be "treatment cycle 1", "treatment cycle 2", "treatment cycle 3", "treatment cycle 4", "treatment cycle 5", "treatment cycle 6", "treatment

cycle 7", "treatment cycle 8", "treatment cycle 9", "treatment cycle 10", "treatment cycle 11", and "treatment cycle 12" for the lead-in and extension study possible treatment regimen cycles.

Demographic and baseline characteristic, disposition, treatment-emergent adverse event (TEAE) for entire study, vital signs, and immunogenicity tables will be summarized under leadin and extension study possible treatment regimens specified in Table 5-3. It will use planned treatment in lead-in study/ planned treatment in extension study for lead-in and extension study possible treatment regimens.

In general, there will be no substitution of missing time or date. However, any partial information will be utilized to its full extent wherever sensible. For example, a medication may be classified as a prestudy medication if the partial information of the medication ending date with only month and year permits a determination that the medication ended prior to the injection date of the study intervention.

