#### 5.3.1. Definition of Endpoints

#### 5.3.1.1. Adverse Events

An AE is defined as any untoward medical occurrence in a participant or clinical investigation participant administered a pharmaceutical product and that does not necessarily have a causal relationship with this treatment.

Per case report form instructions, a new AE record will be created with a new AE onset date for any AE that worsens. Therefore, TEAEs can simply be identified as those AEs with recorded onset date on or after the date of the first study intervention and within 30 days after the study exit.

An AE will be considered a treatment-emergent serious adverse event (TESAE) if it is a TEAE that additionally meets any serious adverse event (SAE) criteria.

A SAE is defined as any AE occurring at any dose that results in any of the following outcomes: death, a life-threatening AE, inpatient hospitalization or prolongation of existing hospitalization, a persistent or significant disability/incapacity, or a congenital anomaly/birth defect. Important medical events that may not result in death, be life-threatening, or require hospitalization may be considered a SAE when, based upon appropriate medical judgment, they may jeopardize the patient or subject and may require medical or surgical intervention to prevent one of the outcomes listed in this definition. All cancer AEs are considered SAEs by Allergan. Abnormal pregnancy outcomes (eg, spontaneous abortion, fetal death, stillbirth, congenital anomalies, ectopic pregnancy) or genetic abnormalities (whether leading to an elective abortion or not) are considered SAEs.

MT10109L-004

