#### 5.3.2. Main Analytical Approach

#### 5.3.2.1. Adverse Events

Adverse events will be coded from the verbatim text into preferred term (PT) and SOC by using the MedDRA dictionary.

For an ongoing AE from the preceding Studies MT10109L-001, -002, -005 and -006 to extension Study MT10109L-004, the onset date, PT, and onset severity will be used to match the same ongoing AE from different studies.

The incidence of AEs will be summarized with frequencies (counts and percentages) by treatment regimen for all events regardless of causality, for all SAEs regardless of causality, and for treatment-related AEs (those with a reasonable possibility of being caused by the study intervention in the investigator's opinion).

The incidence of AEs for all, SAEs (see Section 5.3.1 for definition), and treatment-related AEs will be presented and summarized by MT10109L cycle and over the entire study as follows unless otherwise specified:

1. Overall incidence of TEAEs:

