# 6.4.5. Missing Date Information for Adverse Events

Partial AE onset date will be imputed as follows: 1) if day is missing but month is not, impute the date as the first day of the month; 2) if both day and month are missing, impute the date as 01 Jan; 3) if imputed onset date is before the first intervention, yet the corresponding AE was not observed pretreatment, then impute the onset date as the first treatment date. Imputed partial AE onset date will only be used to determine the AE onset cycle.

Other partial AE dates will not be imputed. All partial dates will be listed "as is" in the data listings. If both AE onset date and first injection of MT10109L date's time are recorded, datetime will be used for imputation in lead in study.

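### The maximum-severity TEAE table is given two incompatible layouts, and on the visible text a TEAE starting after study exit may belong to no treatment cycle

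*SAP*

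**What the plan says.** **Maximum-severity table.** SAP 5.3.2.1 introduces its AE summaries by saying that they "will be presented and summarized by MT10109L cycle and over the entire study as follows unless otherwise specified". Item 3, on maximum severity by preferred term within system organ class, then sets its own layout twice. Its first sentence confines the summary to the entire study. Its last sentence confines the same summary to a presentation by MT10109L cycle. Each sentence is worded as exclusive.

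Protocol 9.4.2.1 says that TEAEs "will be tabulated by system organ class and preferred term and by system organ class, preferred term, and severity", without mentioning cycles. Its next sentence, on treatment-related TEAEs, says that those are "tabulated by system organ class and preferred term by MT10109L cycle".

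**End of the last cycle.** SAP 5.1.1 starts a study treatment cycle on the day of treatment and has it "end on the day prior to the next study intervention or on the study exit day if there are no subsequent interventions". SAP 5.3.1.1 identifies TEAEs as AEs with onset "on or after the date of the first study intervention and within 30 days after the study exit". The protocol agrees on the cut-off: "An adverse event that occurs more than 30 days after study exit will not be counted as a TEAE". Protocol 8.3.1 collects AEs "until 30 days after the participant's last study visit".

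The SAP places AEs in cycles by onset. Section 6.4.5 says "Imputed partial AE onset date will only be used to determine the AE onset cycle", and the by-subject listing in 5.3.2.1 has a field for the treatment cycle of each AE.

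**The concern.** The study's stated objective is the long-term safety of repeat treatments. The by-cycle AE tables are where a reader would look for a change in events as treatments accumulate.

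For the severity table, a programmer has to disobey one of two explicit instructions. The choice would then be made outside the SAP, for a table that supports a primary safety endpoint.

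For the cycles, an event can be a TEAE by definition and still fall after the end of every cycle. Following the text, it would be counted in the entire-study table, left out of every by-cycle table, and listed with an empty cycle field. The two sets of tables would then not reconcile. The gap falls only on last cycles, so it is uneven across the cycle columns.

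**Working it through.** **Severity table.** No arithmetic applies, so I compared the sentences.

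- Item 3, first sentence: entire study, exclusively.
- Item 3, last sentence: by MT10109L cycle, exclusively.
- The lead-in to SAP 5.3.2.1 defaults to both levels unless otherwise specified. It does not help, because item 3 does specify otherwise, in two incompatible ways.
- Protocol 9.4.2.1 attaches the by-cycle layout to the treatment-related table and not to the severity table. This favours the entire-study reading.

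**Cycle gap: inputs.**

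- Exit visit for completers: Day 720 (SAP 1.2; protocol 4.1).
- Latest permitted intervention: Day 690 (SAP 1.2).
- Last cycle ends on the exit day (SAP 5.1.1).
- TEAE window ends at exit + 30 days (SAP 5.3.1.1; protocol 9.4.2.1).
- Interventions: up to 3 in the lead-in study (SAP 1) and up to 9 in the extension (SAP 1.2).

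The plan gives no figure of its own to reproduce here.

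**Formulas**, for a completer with last dose on Day d:

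- Last cycle as defined = 720 − d + 1 = 721 − d days.
- TEAE days from the last dose = (720 + 30) − d + 1 = 751 − d days.
- Days with no cycle = (751 − d) − (721 − d) = 30, namely Days 721 to 750.
- Share of post-dose TEAE days with no cycle = 30 / (751 − d).

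| Last dose (d) | Last cycle, days | TEAE days from last dose | Share with no cycle |
|---|---|---|---|
| Day 690 | 31 | 61 | 30/61 = 49.2% |
| Day 660 | 61 | 91 | 30/91 = 33.0% |
| Day 540 | 181 | 211 | 30/211 = 14.2% |
| Day 360 | 361 | 391 | 30/391 = 7.7% |
| Day 1 | 720 | 750 | 30/750 = 4.0% |

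For a participant who exits early, k days after the last dose, the share is 30 / (k + 31).

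**Which columns are exposed.** At most 3 + 9 = 12 interventions are possible, so no dose can follow cycle 12 and it is always a last cycle. Every participant in that column has up to 30 unassigned days. In earlier columns, only participants whose treatment stopped there have them.

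**After the fix.** With the last cycle run to exit + 30 days, the unassigned days fall from 30 to 0, and a cycle starting on Day 690 lasts 61 days instead of 31.

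**The case against.** The strongest case against the cycle point is one of terms and missing text. SAP 5.1.1 defines a study treatment cycle, whereas the AE tables are laid out by MT10109L cycle, which has no separate definition in the visible text. The two need not coincide, because a lead-in intervention could be placebo (SAP Table 4-1). SAP 5.1.2 to 5.1.3, Table 5-3 and part of Table 4-1 are not visible, protocol 9.4.2.1 opens with a gap, and table specifications sit in a separate document. A rule for post-exit events may exist there. All of this stands, and it makes the cycle point conditional. It does not remove it: two stated rules still end on different days, and the listing uses the treatment-cycle term itself.

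The second objection concerns size. The shares above are calendar days, not events. No visit after Day 720 is visible, and protocol 8.3.1 does not oblige investigators to seek AE information actively once participation has ended. Collection does continue for 30 days after the last visit, but those days may not be observed as closely as in-study days. This also stands.

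A reader might infer that events after the last dose are always undercounted in the cycle 12 column, or that about half of them are lost. The documents support neither. An undercount needs a TEAE to occur after exit, no event rate is given, and 49% holds only for a dose on the last permitted day.

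On the severity table, the fair objection is that the conflict is editorial and that the protocol already points to one reading. The protocol sentence ends without a full stop and may be cut short, so it favours the entire-study layout without settling it.

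**Conclusion.** Both points hold, and both are minor.

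The severity-table contradiction is certain on the visible text and depends on nothing hidden. The entire-study layout is the better supported of the two.

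The cycle gap holds if the MT10109L cycle of the AE tables ends where SAP 5.1.1 ends a treatment cycle, and if no AE-specific rule exists in text that is not visible. On those assumptions, up to 30 TEAE days per participant have no cycle, always at the end of the last cycle. The number of events affected cannot be derived, because the documents give neither the spread of last-dose days nor an event rate; it may be small.

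It would be wrong to conclude that the primary AE result is compromised. The primary variable, presence of TEAEs (SAP 1.1), is also summarised over the entire study. That incidence counts post-exit events, and they stay in the listing with their start dates. Post-exit TEAEs would be missing from all severity summaries only if the less supported by-cycle layout were used alone and the cycle assumption also held.

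**What to change.** 1. In SAP 5.3.2.1 item 3, delete the closing sentence that restricts the table to a by-cycle layout. Present maximum severity over the entire study, with a by-cycle version as an optional addition.
2. In SAP 5.1.1, state that for AE summaries and listings the last cycle, meaning both the last treatment cycle and the last MT10109L cycle, runs to study exit + 30 days. If such a rule already exists elsewhere, cross-refer to it instead. Limiting the rule to AE outputs leaves the cycle definition unchanged for exposure, vital signs and efficacy.

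The cost is two SAP wording edits and one derivation rule. No protocol change, new assessment or change to the TEAE or TESAE definitions is needed. The one downside is that last-cycle AE counts may rise slightly.

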6.4. Study Intervention Compliance

Participants will receive all doses under the direct supervision of study site personnel. Study intervention compliance will not be calculated.

The study site will keep an accurate drug disposition record that specifies the amount of study intervention administered to each participant and the date of administration.

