8.3.7. Medication Errors

Medication error refers to any unintended error in the dosing and/or administration of the study intervention as per instructions in the protocol. Medication errors generally fall into 4 categories as follows:

- Wrong study intervention
- Wrong dose (including dosing regimen, strength, form, concentration, amount)
- Wrong route of administration
- Wrong participant (ie, not administered to the intended participant)

Medication errors include occurrences of overdose and underdose of the study intervention.

Overdose: Unintentional administration of a quantity of the study intervention given per administration or per day that is above the maximum recommended dose according to the reference safety information or protocol for the study intervention or comparator as applicable. See Section 8.4 for information on the treatment of overdose.

Underdose: Unintentional administration of a quantity of the study intervention given per administration or per day that is under the minimum recommended dose according to the protocol.

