## 5. Statistical Analyses

## 5.1. General Considerations

[figure not shown]
The proportions of participants who achieve the efficacy endpoints will be summarized with frequency tables. The 95% CI for responders will be estimated based on the observed data by intervention group and by treatment cycle. For the US FDA, efficacy analyses will be based on the ITT population.

The safety analyses will be based on the ITT population.

Statistical analyses will be performed using version 9.4 (or newer) of statistical analysis software (SAS) on a Linux operating system.

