#### 5.1.9. Study Intervention

If "Was the subject injected per protocol?" ticked as yes, the dose used of each injection will follow per protocol section 6.1.2 in extension period.

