## 5.3. Primary Endpoints Analysis

The primary endpoints are incidence of AEs, change from baseline in vital sign parameters, and presence of binding and neutralizing antibodies for safety.

[figure not shown]

MT10109L-004

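### SAP 5.1.1 groups the entire-study TEAE, vital-sign and immunogenicity tables by planned treatment, and no as-received rule is visible

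*SAP*

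**What the plan says.** SAP 5.1.1 lists the tables to be shown by lead-in/extension regimen. Besides demographics and disposition, the list includes "treatment-emergent adverse event (TEAE) for entire study" and continues: "vital signs, and immunogenicity tables will be summarized under leadin and extension study possible treatment regimens specified in Table 5-3". The next sentence states how a participant gets a column: "It will use planned treatment in lead-in study/ planned treatment in extension study for lead-in and extension study possible treatment regimens".

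SAP 5.3 shows what these tables carry: "The primary endpoints are incidence of AEs, change from baseline in vital sign parameters, and presence of binding and neutralizing antibodies for safety". SAP 5.1 sets the population: "The safety analyses will be based on the ITT population". By Table 4-1, ITT means enrolled in MT10109L-004 with at least one intervention, MT10109L or placebo, in the lead-in or in the extension. SAP 1 adds that enrolled participants are analysed whether or not they are treated.

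On what was actually given, Protocol 8.3.7 foresees errors of intervention, dose, route and participant; one category reads "Wrong dose (including dosing regimen, strength, form, concentration, amount)". Protocol 6.4 requires an "accurate drug disposition record that specifies the amount of study intervention administered to each participant". SAP 5.1.9 says that where the site ticks yes to per-protocol injection, "the dose used of each injection will follow per protocol section 6.1.2 in extension period". The available text does not say what happens when the answer is no.

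**The concern.** The study's stated objective is the long-term safety of repeated MT10109L. It tests no hypothesis and the extension is not randomized. The usual reason for grouping by planned treatment, to protect a randomized comparison, therefore does not apply to this study's own objective. In a safety table the column heading tells the reader what the people in it were exposed to. Under the planned rule that statement can be wrong in two ways.

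- **Wrong product in the lead-in.** A participant planned for placebo but given MT10109L, or the reverse, keeps the planned label, and all their events and antibody results go with it.
- **Never injected in the extension.** Extension treatment depends on meeting retreatment criteria (Protocol 6.6, SAP 1.2), so a participant can be in ITT on lead-in treatment alone. That participant still carries a planned extension label of MT10109L. This needs no error by anyone.

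The AE tables will not reliably reveal a dosing error either. Protocol 10.3.1 does not treat an overdose in itself as an AE unless it was intentional with possible self-harm intent.

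**Working it through.** **Step 1. Reading the rule.** The documents give no misallocation rate, and there is no power or event figure to reproduce: about 800 is an anticipated roll-over number without a formal calculation. The claim is about classification, so it is checked by setting the texts side by side.

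| Question | Where | Answer |
|---|---|---|
| Which safety tables use planned regimens? | SAP 5.1.1 | Entire-study TEAEs, vital signs, immunogenicity |
| Do they carry the primary endpoints? | SAP 5.3 | Yes, all three |
| Is there an as-treated safety population or sensitivity table? | SAP 4, 5.1 | None visible; safety uses ITT |
| Can ITT include someone untreated in the extension? | SAP 1, Table 4-1 | Yes |
| Is the amount given recorded? | Protocol 6.4, SAP 5.4.1.1 | Yes |
| Are AE tables by MT10109L cycle under the rule? | SAP 5.1.1, 5.3.2.1 | Planned, but not named in it |
| Are regimens defined by area or dose? | Table 5-3 | Not visible |

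As a consistency check on the cycle count, up to 3 lead-in interventions plus up to 9 extension interventions gives 3 + 9 = 12, which matches the 12 named cycles.

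**Step 2. Average effect (illustration).** Let e be the share of a column whose received regimen differs from the planned one. Let p be the event rate under the labelled regimen and q the rate under what was actually received.

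Observed rate = (1 − e) × p + e × q, so the shift is −e × (p − q).

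Take p = 3%, the highest expected rate in Protocol Tables 8-1 and 8-2 (eyelid ptosis, from another product's data). Take q = 0%, which gives the largest downward shift. The values of e are assumptions.

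| e (assumed) | Participants of 800 | Observed rate | Shift, points |
|---|---|---|---|
| 0.5% | 4 | 0.995 × 3% = 2.985% | −0.015 |
| 1% | 8 | 0.99 × 3% = 2.97% | −0.03 |
| 2% | 16 | 0.98 × 3% = 2.94% | −0.06 |
| 5% | 40 | 0.95 × 3% = 2.85% | −0.15 |

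For scale, the 95% half-width of a 3% rate is 1.96 × √(0.03 × 0.97 / n). That is 1.18 points at n = 800. It is 2.05 points at n = 267, which is 800 / 3, assuming the three planned arms of Protocol Appendix 6 are equal in size. Every shift in the table is well inside these widths.

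**Step 3. One participant in the wrong column.** One case moves a column's rate by 1 / 800 = 0.125 points, or 1 / 267 = 0.375 points (about 0.37 to 0.38). Those figures are also small. For a rare finding, however, the reader looks at the count: a column with no neutralizing-antibody case becomes a column with one, or the reverse.

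**The case against.** The strongest reply is that the rule is narrow, its effect slight, and other output shows what was given. Much of this stands.

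- **By-cycle tables.** A reader might infer that every primary safety table uses planned treatment. The documents do not support that. SAP 5.3.2.1 also plans AE tables by MT10109L cycle, a cycle begins on the day of injection, and Table 4-1 has a column on study treatment by cycle whose content is not visible. Their rule may be stated there.
- **Wrong area or dose.** A reader might infer that these errors also put a participant in the wrong column. That requires Table 5-3 to define regimens by area or dose. Area is plausible, given three arms and treatment of the same areas as in the lead-in. If the regimens are only placebo or MT10109L sequences, the label stays correct. Wrong area is also not one of the four named error categories.
- **SAP 5.1.9.** A reader might infer that it masks misdosing. It does not: it applies the protocol dose only where the site recorded the injection as per protocol.
- **Toxin-free columns.** All participants are planned for MT10109L in the extension, so no planned regimen is free of it. A wrong product therefore matters mainly in the lead-in part.
- **Other output.** Significant deviations are summarized and listed, the AE listing gives treatment dates and cycle, and exposure is counted from injections. All doses are supervised and given by experienced physicians.

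SAP 5.3.2.2 also says vital signs are shown by study intervention, without saying planned or received.

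What does not fall is the explicit rule itself. Listings and exposure tables do not correct the column in which a primary safety result is reported.

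**Conclusion.** The point holds for the entire-study TEAE, vital-sign and immunogenicity tables. As written, a participant given the wrong product in the lead-in, or never injected in MT10109L-004, is reported under a regimen not received. The available text has no as-received rule or sensitivity table to offset this.

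The likely numerical effect is small: 0.015 to 0.15 percentage points on a 3% event. That range rests on an assumed misallocation of 0.5% to 5% and a zero event rate under the treatment actually received. The documents do not give the number of participants affected, whether by error or by never being injected. The practical reason to act is that one rare event or one neutralizing-antibody case could sit in the wrong column of a primary table. This does not threaten the study's overall safety conclusion, but it is an avoidable misclassification in a study whose purpose is safety, and it should be corrected. The conclusion does not extend to the by-cycle AE tables, nor, without Table 5-3, to wrong area or wrong dose.

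**What to change.** In SAP 5.1.1:

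- Define the regimen columns of the entire-study TEAE, vital-sign and immunogenicity tables by treatment actually received in the lead-in and in the extension. Include a category for participants not treated in the extension, and one line on how to classify a participant who received both products in the lead-in by error.
- Keep planned treatment for demographics and disposition.
- List every participant whose received treatment differs from planned, including those never injected in MT10109L-004.
- If Table 4-1 does not already do so, state how treatment is assigned in the by-cycle AE tables.

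In SAP 5.1.9, leave the rule for injections recorded as per protocol unchanged. State that where the injection was not per protocol, the analysis uses the recorded administered amount.

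The cost is SAP wording plus one actual-treatment variable built from administration records that the sites already keep. No trial procedure changes. The one drawback is that a few participants may sit in different columns in the demographic and safety tables; a footnote giving the number and reason is enough.
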